10.9 CLINICAL TRIAL TERMINATION

The principal investigator(s) will be notified in writing upon termination of the clinical trial. The Trial Sponsor retains the right to suspend or terminate this clinical trial at any time. Upon trial termination, the Investigator will contact the trial subjects to perform a final follow-up assessment within 2 months of trial termination. If a subject completed a protocol scheduled clinical evaluation within 6 months prior to trial termination, the final follow-up assessment may be completed by telephone. Subjects should continue seeing their physicians as part of routine clinical follow-up after heart valve replacement surgery.

11 ADVERSE EVENTS

11.1 REPORTING PROCEDURE

Adverse event information will be reported throughout the clinical trial as they occur. Adverse events will be followed until they are adequately resolved or explained. The investigator(s) should report any serious adverse event to the Trial Sponsor's Clinical Research department within 48 hours after the investigator's first knowledge of the event, followed by a written report in ten working days. **Notification should be done via email to [contact] or faxed to [contact].** In addition, trial sites will

report all adverse events to their local EC in accordance with the review committee's requirements.

11.2 ADVERSE EVENT DEFINITIONS

11.2.1 ADVERSE EVENT

An adverse event (AE) is defined in ISO 14155:2011 (referred to hereafter as ISO 14155) as any untoward medical occurrence in a subject.

11.2.2 ADVERSE DEVICE EFFECT

An adverse device effect (ADE) is defined in ISO 14155 as any untoward or unintended response to a medical device. This definition includes any event resulting from insufficiencies or inadequacies in the instructions for use or the deployment of the device or any event that is a result of user error.

11.2.3 SERIOUS ADVERSE EVENT

A serious adverse event (SAE) is defined in ISO 14155 as an adverse event that: led to death, led to a serious deterioration in the health of the subject that resulted in a life-threatening illness or injury, resulted in a permanent impairment of a body structure or a body function, required inpatient hospitalization or prolongation of existing hospitalization, or resulted in medical or surgical intervention to prevent permanent impairment to body structure or a body function, or led to fetal distress, fetal death or a congenital abnormality or birth defect.

11.2.4 SERIOUS ADVERSE DEVICE EFFECT

A serious adverse device effect (SADE) is defined in ISO 14155 as an adverse device effect that resulted in any of the consequences characteristics of a serious adverse event or that might have led to any of these consequences if suitable action had not been taken or intervention had not been made or if circumstances had been less opportune.

11.2.5 UNANTICIPATED SERIOUS ADVERSE DEVICE EFFECT

An unanticipated serious adverse device effect (USADE) is defined as serious adverse device effect, which by its nature, incidence, severity or outcome is not identified in the Clinical Investigator's Brochure.

11.3 DEATHS AND EXPLANTS

11.3.1 SUBJECT DEATHS

In the event of subject death, every effort should be made to obtain a copy of the autopsy report and/or death summary. Information on the cause of death and its relationship to the device used in this clinical trial will be determined by the principal investigator. Copies of an autopsy report, if available, and/or a death summary are to be sent to the Trial Sponsor.

If a device is explanted during autopsy, the device should be returned to the Trial Sponsor for analysis. Return kits for devices will be provided upon request by the clinical monitor.

11.4 CLINICAL EVENTS COMMITTEE

The Clinical Events Committee (CEC) evaluates adverse events that are endpoint related. The CEC adjudicates events for their relatedness to the investigational device and/or the surgical procedure. The CEC will be composed of physicians familiar with the treatment of valvular heart disease and cardiac surgery who are not participating in the investigational trial.

The trial Sponsor will provide the CEC completed case report forms and any relevant source documentation/subject information as provided by the clinical site investigators. Trial Sponsor will insure that all information is de-identified before presenting to the committee. The CEC documents its findings or rulings on each event. All meeting minutes and supporting documentation are maintained by the CEC administrator with a copy provided to the trial Sponsor.

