7.3 ENDPOINTS

7.3.1 SAFETY ENDPOINTS

Descriptive information of early rates and late linearized rates of the following:

- Structural valve deterioration
- Thromboembolism
- All bleeding/hemorrhage
- Major bleeding/hemorrhage
- All paravalvular leak
- Major paravalvular leak
- Non-structural valve dysfunction
- Endocarditis
- Hemolysis
- All cause mortality
- Trial valve-related mortality
- Explant

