9.3 SAFETY ANALYSIS

Early adverse events within 30 days of procedure will be reported as the number of events divided by the number of enrolled subjects. Linearized rates will be used to summarize adverse events for the late (>30 days) post-operative period. The linearized rates will be calculated as the number of late events divided by the total number of late-subject years.

Percentages for the early events and linearized rates for the late events also will be calculated for all other complications observed in the trial.

Actuarial rates based on the method of Kaplan-Meier will be calculated for each of the safety endpoints at each of the follow-up time points.

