12 TRIAL AND DATA MANAGEMENT

12.1 TRIAL CORE LABS

12.1.1 ECHOCARDIOGRAPHY CORE LAB

The Echo Core Lab is responsible for independently evaluating echocardiograms submitted preoperatively and postoperatively by trial sites, and for reporting of hemodynamic and other valvular function results. Echocardiograms will be sent directly from the investigational sites to the Echo Core Lab. See **Appendix 15.7** for the Echo Core Lab Manual.

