AE148	AV BLOCK I: A CONDUCTION DISORDER OF NERVOUS IMPULSE AT THE LEVEL OF THE ATRIOVENTRICULAR JUNCTION, I.E. BETWEEN ATRIUM AND VENTRICLE.
AE149	" AV BLOCK II: THERE ARE TWO TYPES: MOBILT I PROGRESSIVE PROLONGATION OF PR INTERVAL WITH DROPPED BEATS (THE PR INTERVAL GETS LONGER AND LONGER; FINALLY ONE BEAT DROPS) MOBILT II PR INTERVAL REMAINS UNCHANGED PRIOR TO THE P-WAVE WHICH SUDDENLY FAILS TO CONDUCT TO THE VENTRICLES;
AE150	" AV BLOCK III: NO P-WAVES CONDUCT TO THE VENTRICLE AND AV DISSOCIATION IS COMPLETE. ANY LEVEL OF AV BLOCK EVENT SHOULD BE DOCUMENTED AND CONFIRMED BY ECG TEST RESULTS.

AE CODE LIST	
CODE	DEFINITION
AE145	ARRHYTHMIA - BUNDLE BRANCH BLOCK - LEFT
AE.2	CARDIOVASCULAR – ARRHYTHMIA (CONTINUED)
AE146	ARRHYTHMIA - BUNDLE BRANCH BLOCK - RIGHT
AE147	ARRHYTHMIA - SUPRAVENTRICULAR TACHYCARDIA (SVT)
AE148	ARRHYTHMIA - PAROXYSMAL ATRIAL TACHYCARDIA (PAT)
AE150	ARRHYTHMIA - VENTRICULAR FIBRILLATION
AE151	ARRHYTHMIA - TACHYCARDIA - VENTRICULAR
AE152	ARRHYTHMIA - TACHYCARDIA - NON-VENTRICULAR
AE153	ARRHYTHMIA - BRADYCARDIA
AE154	ARRHYTHMIA - TACHY-BRADYCARDIA
AE155	ARRHYTHMIA - PACEMAKER/ICD MALFUNCTION
AE156	ARRHYTHMIA - OTHER
AE.3	CARDIOVASCULAR - REGURGITATION
	IF THE VALVE INVOLVED IS THE STUDY VALVE, THEN THIS DEFINITION SHOULD BE USED, BUT THE EVENT SHOULD BE REPORTED AS STRUCTURAL OR NON-STRUCTURAL VALVE DYSFUNCTION (AS APPROPRIATE) REGURGITATION, AORTIC: ALSO KNOWN AS AORTIC INSUFFICIENCY AND INCOMPETENCE OF THE AORTIC VALVE, IN WHICH A PORTION OF THE LEFT VENTRICULAR FORWARD STROKE VOLUME RETURNS TO THE CHAMBER DURING DIASTOLE. THIS CATEGORY DOES NOT INCLUDE PARAVULVAR LEAK, WHICH SHOULD BE CAPTURED UNDER NON-STRUCTURAL VALVE DYSFUNCTION. REGURGITATION, CENTRAL: OCCURS WHEN THE VALVE LEAFLETS DO NOT COMPLETELY CLOSE AND ALLOW SOME BLOOD TO LEAK BACK INTO THE HEART. REGURGITATION, INDETERMINATE: OCCURS WHEN BLOOD LEAKS BACK INTO THE HEART AND CANNOT BE CATEGORIZED BY LOCATION AND OR SEVERITY. REGURGITATION, MITRAL: ALSO KNOWN AS MITRAL INCOMPETENCE AND MITRAL INSUFFICIENCY IN WHICH THE BLOOD FLOWS BACKWARDS THROUGH THE MITRAL VALVE EACH TIME THE LEFT VENTRICLE CONTRACTS. DIAGNOSED BY AUSCULTATION (MURMUR) OR ECHOCARDIOGRAPHY. REGURGITATION, TRICUSPID: INSUFFICIENCY OF THE TRICUSPID VALVE CAUSING BLOOD FLOW FROM THE RIGHT VENTRICLE TO THE RIGHT ATRIUM DURING SYSTOLE.
AE160	REGURGITATION - AORTIC-CENTRAL/TRANSVALVULAR-+1
AE161	REGURGITATION - AORTIC-CENTRAL/TRANSVALVULAR-+2

Clinical Investigational Plan
Protocol Number: 2010-03

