	SHORT TIME.
AE.12	PSYCHIATRIC (CONTINUED)
AE434	PSYCHIATRIC – OTHER
AE.13	MUSCULAR SKELETAL/ DERMATOLOGIC
AE450	STERNAL WOUND/THORACIC INFECTION
AE451	BONE FRACTURE/BREAK
AE452	WOUND INFECTION – OTHER
AE454	INFECTION/INFLAMMATION - OTHER
AE456	MUSCULAR SKELETAL / DERMATOLOGIC - OTHER
AE.14	NONSPECIFIC, UNKNOWN, OR OTHER BODY SYSTEM
AE470	ANAPHYLACTIC REACTION
AE471	ALLERGIC REACTION – MEDICATION RELATED
AE472	ALLERGIC REACTION – OTHER
AE473	CANCER – PROGRESSION OF UNDERLYING DISEASE
AE474	CANCER – NEWLY DIAGNOSED
AE475	HEARING DISORDER
AE476	MULTI-SYSTEM ORGAN FAILURE
AE477	SPEECH DISORDER
AE479	VISION DISORDER
AE480	FEVER - UNKNOWN ORIGIN

AE CODE LIST	
CODE	DEFINITION
AE481	NONSPECIFIC, UNKNOWN, OR OTHER BODY SYSTEM - OTHER COMPLICATION
AE.15	DEVICE DYSFUNCTION
AE500	SVD - STUDY VALVE WEAR
AE501	SVD - STUDY VALVE FRACTURE
AE502	SVD - STUDY VALVE POPPET ESCAPE
AE503	SVD - STUDY VALVE CALCIFICATION
AE504	SVD - STUDY VALVE LEAFLET TEAR
AE505	SVD - STUDY VALVE STENT CREEP
AE506	SVD - STUDY VALVE SUTURE LINE DISRUPTION
AE507	SVD - STRUCTURAL VALVE DETERIORATION, OTHER
AE525	SVD - ANNULAR FRAME DAMAGE
AE526	SVD - ANNULAR FRAME SEPARATION
AE527	SVD - STENT FRAME FRACTURE
AE528	SVD - STENT FRAME DEFORMATION
AE529	SVD - STENT FRAME SEPARATION
AE512	NSD - ENTRAPMENT BY PANNUS, TISSUE, OR SUTURE
AE164	NSD - PARAVALVULAR LEAK - +1
AE165	NSD - PARAVALVULAR LEAK - +2
AE166	NSD - PARAVALVULAR LEAK - +3
AE167	NSD - PARAVALVULAR LEAK - +4
AE176	NSD - STUDY VALVE STENOSIS - MILD

ANY COMPLICATION THAT CANNOT OTHERWISE BE CATEGORIZED REQUIRING HOSPITALIZATION OR MEDICAL INTERVENTION.

INCLUDES DYSFUNCTION OR DETERIORATION INVOLVING THE OPERATED VALVE (EXCLUSIVE OF INFECTION OR THROMBOSIS). THE TERM STRUCTURAL VALVE DETERIORATION REFERS TO CHANGES INTRINSIC TO THE VALVE SUCH AS: WEAR, FRACTURE, CALCIFICATION, LEAFLET TEAR, MANUFACTURED SUTURE LINE DISRUPTION

"

"

"

"

"

"

"

"

"

"

"

"

"

"

"

ANY ABNORMALITY NOT INTRINSIC TO THE VALVE (DO NOT DIRECTLY INVOLVE VALVE COMPONENTS) ITSELF THAT RESULTS IN STENOSIS OR REGURGITATION OF THE OPERATED VALVE OR HEMOLYSIS (EXCLUDES THROMBOSIS AND INFECTION). EXAMPLES INCLUDE: ENTRAPMENT BY PANNUS, TISSUE, OR SUTURE, PARAVALVULAR LEAK, INAPPROPRIATE SIZING, INAPPROPRIATE POSITIONING, REGURGITATION AS A RESULT OF TECHNICAL ERROR, STJ DILATION, DILATION OF THE VALVE ANNULUS, OBSTRUCTION OF THE CORONARY OSTIA BY THE STUDY VALVE.

LEAKAGE BETWEEN THE SEWING RING AND THE ANNULUS.

"

"

"

"

NSD "

Clinical Investigational Plan

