Visit Name Subevent# CRF Name Blank CRF

Please indicate the Paravalvular Leak Severity:

Please indicate the Number of Jets:

Please specify:

Please indicate the location of the jets:

Please indicate the image views of the jets:

PLAX No Yes

PSAX No Yes

A5C No Yes

A3C No Yes

Please indicate the Transvalvular Leak Severity:

Please indicate the total regurgitation severity:

Aortic Valve Morphology

Please indicate the leaflet mobility:

Please indicate the leaflet thickening:

Please indicate the degree of calcification:

Please indicate whether the following morphologies were observed:

Cusp Perforation No Yes Indeterminate

Pannus Formation No Yes Indeterminate

Thrombus No Yes Indeterminate

Vegetation No Yes Indeterminate

Ring Abscess No Yes Indeterminate

Pseudoaneurysm No Yes Indeterminate

Study Doc#

Subject ID Site Visit Date Status

Visit Name Subevent# CRF Name Blank CRF

Non-Aortic Valve Regurgitation

Please indicate the level of Tricuspid Valve Regurgitation:

Please indicate the level of Mitral Valve Regurgitation:

Pericardial Effusion

Please indicate the level of Pericardial Effusion:

Please specify:

RV Function

Please indicate overall assessment of the Right Ventricle:

ECHO Quality

Please indicate the overall Quality of the ECHOs:

Comments

Study

Doc#

Subject ID

Site

Visit Date

Status

Visit Name

Subevent#

CRF Name

Blank CRF

PROTOCOL DEVIATION (Baseline)

Rev B

Date of Deviation

(DD/MMM/YYYY)

Please select type of deviation

Please describe the type of deviation

What was the reason for the deviation?

Please specify:

Please indicate the corrective action taken to prevent further deviations

Please specify:

Study

Doc#

Subject ID

Site

Visit Date

Status

Visit Name

Subevent#

CRF Name

Blank CRF

PROTOCOL DEVIATION (Discharge)

Version A

Date of Deviation

(DD/MMM/YYYY)

Please select type of deviation

Please describe the type of deviation

What was the reason for the deviation?

Please specify

Please indicate the corrective action taken to prevent further deviations

Please specify

Study

Doc#

Subject ID

Site

Visit Date

Status

Visit Name

Subevent#

CRF Name

Blank CRF

PROTOCOL DEVIATION (Procedure)

Version A

Date of Deviation (DD/MMM/YYYY)

Please select type of deviation

Please describe the type of deviation

What was the reason for the deviation?

Please specify

Please indicate the corrective action taken to prevent further deviations

Please specify

Study Doc#

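### No rule links the core lab's paravalvular-leak grades to the leak and valve-dysfunction safety endpoints, so those rates can depend on which leaks the sites file as adverse events

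*Combined protocol and SAP*

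**What the plan says.** Section 7.3.1 lists All paravalvular leak, Major paravalvular leak and NSVD among the safety endpoints, introduced as "Descriptive information of early rates and late linearized rates of the following".

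Section 9.3 gives the numerators. For the early period: "Early adverse events within 30 days of procedure will be reported as the number of events divided by the number of enrolled subjects". For the late period: "Linearized rates will be used to summarize adverse events for the late (>30 days) post-operative period", with late subject-years as the denominator. Kaplan-Meier rates are added for each safety endpoint.

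Appendix 15.1 makes paravalvular leak an adverse event code within non-structural dysfunction. Codes AE164 to AE167 run from "NSD - PARAVALVULAR LEAK - +1" up to +4. Regurgitation or stenosis of the study valve is also to be filed as structural or non-structural dysfunction. In Appendix 15.3, the Assessment form asks the site to complete one adverse event form per event.

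Section 11.4 describes the Clinical Events Committee (CEC): "The Clinical Events Committee (CEC) evaluates adverse events that are endpoint related". It rules on relatedness to the device or procedure. It works from completed case report forms and from documents that the sites supply.

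Section 12.1.1 makes the core lab responsible for independent reading and "for reporting of hemodynamic and other valvular function results". The Echo Manual (Appendix 15.6) has it grade paravalvular leak on full transthoracic, transesophageal and abbreviated transthoracic studies. The Echo Core Lab Results form in Appendix 15.3 has the field "Please indicate the Paravalvular Leak Severity". The only endpoint that names the core lab is the hemodynamic performance endpoint in 7.3.2. The only planned summary of regurgitation level is in 9.4.

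**The concern.** Two readings of the same valve are collected. The implanting site's reading counts towards the safety rate if the site files an adverse event. The core lab's reading is independent and already recorded, but its only stated analytical use is in performance. The plan does not say what happens when the core lab grades a leak and no adverse event form exists, or when the two grades differ.

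The trial is uncontrolled, and these descriptive rates are its safety result. No comparator arm would share, and so offset, any under-filing. With up to 6 sites, differences in filing habit could also look like differences in outcome. All paravalvular leak is the most exposed endpoint, because it includes the lowest grade. NSVD moves with it, because the leak codes are NSVD codes.

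**Working it through.** **No planned figure to reproduce.** Section 9.1 gives only a maximum of 200 subjects. No expected leak rate, margin, alpha or power is stated. The check is therefore a trace of the data path, followed by an illustration.

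**Data path, step by step**

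| Step | Site route | Core-lab route |
|---|---|---|
| Leak observed | Site echo or examination | Central reading of the study echo (12.1.1, 15.6) |
| Recorded | Adverse event form, AE164 to AE167 (15.1, 15.3) | Echo Core Lab Results form (15.3) |
| Adjudicated | CEC, for relatedness, once an event exists (11.4) | No rule stated |
| Analysed | Safety rates (9.3) | Performance endpoint and summary (7.3.2, 9.4) |

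No section crosses from the right-hand column to the left. The CEC step starts from an adverse event, so a subject with no filed event gives it nothing to review.

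The two outputs also differ in kind. Section 9.3 counts events over enrolled subjects or late subject-years. Section 9.4 gives the distribution of regurgitation level at each visit in implanted subjects. It does not say whether paravalvular leak is shown separately from transvalvular leak, although the core-lab form grades both as well as the total.

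**Illustration (early proportion)**

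Inputs:
- N = 200, the maximum in 9.1.
- p = share of subjects in whom the core lab sees leak. **Assumed** 5%, 10% or 15%.
- f = share of those leaks that sites file. **Assumed** one half.

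Formula: reported rate = (N × p × f) / N = p × f. The intervals are exact (Clopper-Pearson) 95% limits, added only to show scale; section 9.3 plans none.

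| p | Leaks seen (200 × p) | Filed at f = 0.5 | Reported rate | 95% interval | Contains p? |
|---|---|---|---|---|---|
| 5% | 10 | 5 | 2.5% | 0.8% to 5.7% | Yes |
| 10% | 20 | 10 | 5.0% | 2.4% to 9.0% | No |
| 15% | 30 | 15 | 7.5% | 4.3% to 12.1% | No |

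Varying f at p = 10%:
- f = 0.75: 15 events, 7.5% (4.3% to 12.1%), which contains 10%.
- f = 0.25: 5 events, 2.5% (0.8% to 5.7%), which does not.
- f = 1: 20 events, 10% (6.2% to 15.0%), and no bias.

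The NSVD event count falls by the same number of unfiled leaks. Late leaks are reported per subject-year, so these percentages do not carry over to the late rates, but the proportional loss would be the same.

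**The case against.** The strongest reply is that this is silence, not a defect. The plan never says that core-lab results are withheld from the sites or the CEC. The core-lab form is itself one of the case report forms, and the CEC receives completed case report forms. The adverse event form lists echocardiogram as a method of detection. Section 12.9.2 mentions validation programs, data entry conventions and form instructions that are not reproduced and might contain a reconciliation step. This stands as far as it goes. A reader might infer that core-lab grades feed only the performance tables and that an unfiled leak can never become an endpoint event; the documents do not support that. But being allowed to use the data is not a rule for using it.

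A reader might also infer that site and core-lab disagreement cannot be audited, because the Site Echo Tracking Form is marked as not being a case report form. That goes too far. The Surgery Data form records the site's leak severity at implant, filed leaks carry a grade in their code, the Assessment form points to an echocardiogram form, and test results are kept for the monitor. Nor is the +1 paravalvular code labelled trace; that label belongs to other regurgitation codes.

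It can be said that 9.4 would reveal under-filing anyway. It might hint at it. But per-visit distributions in implanted subjects are not incidence, and they may not separate paravalvular leak.

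Finally, core-lab data have limits of their own. A scheduled echo dates a leak to the visit, not to its onset. At years 2 and 4 an echo depends on a murmur being heard at the site. These limits shape the fix but do not remove the need for it.

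**Conclusion.** The point holds as a possible, not a certain, under-count. As written, the safety rates for paravalvular leak and NSVD rest on adverse events that sites file, and no stated rule lets an independent core-lab finding generate, correct or challenge such an event. Any bias from unfiled leaks is downward and proportional to the share not filed.

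The size is unknown. The 5%, 10% and 15% leak frequencies and the filing share of one half are assumptions; on them the reported early rate is 2.5%, 5% and 7.5%. If every leak is filed, there is no bias.

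All endpoints are descriptive, so no test, type I error or power is affected. A related gap is that the documents do not define which leaks are Major: the leak codes carry grades but no such threshold. The severity options on the core-lab form cannot be read in the available text, so a mapping from core-lab grades to AE164 to AE167 cannot be assumed.

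This is a cheap improvement.

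**What to change.** Add the following to sections 9.3 and 11.4:

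1. **Listing and reconciliation.** From the existing core-lab form, the sponsor lists every finding of new or worse paravalvular leak or transvalvular regurgitation of the study valve and reconciles it with the adverse event forms.
2. **Referral.** Findings with no adverse event form go to the CEC as potential endpoint events. Because its stated task is relatedness, section 11.4 should say that it also rules on whether such a finding counts.
3. **Reporting.** Paravalvular leak incidence by core-lab grade is shown beside the adverse-event-based rate, with the site-filed count.
4. **Major leak.** Before analysis, state on the core lab's own grading scale which grades count as Major.
5. **Stated limits.** Onset is dated to the first echo showing the leak; a leak first seen after 30 days may have begun earlier; at years 2 and 4 an echo is done only if a murmur is heard.

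The cost is protocol and analysis wording plus one data listing, with no new images or readers. The reported leak rate will probably rise, and the CEC will review some more cases.

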12 TRIAL AND DATA MANAGEMENT

12.1 TRIAL CORE LABS

12.1.1 ECHOCARDIOGRAPHY CORE LAB

The Echo Core Lab is responsible for independently evaluating echocardiograms submitted preoperatively and postoperatively by trial sites, and for reporting of hemodynamic and other valvular function results. Echocardiograms will be sent directly from the investigational sites to the Echo Core Lab. See **Appendix 15.7** for the Echo Core Lab Manual.

12.2 DEVICE SHIPMENTS

An initial set of Edwards's aortic valve, Model 11000 will be shipped to the trial site once the following conditions are met: the trial site has obtained Ministry of Health and Ethics Committee approval, a signed Clinical Trial Agreement is in place, and the Site Initiation Visit, including Principal Investigator training, has been completed. Additional devices will be sent to the trial site as devices are used or as needed.

12.3 INVENTORY AND ACCOUNTABILITY RECORDS

All device shipments will have inventory and shipment records. Devices may be hand carried to participating trial sites by Trial Sponsor personnel. Shipment will be accompanied by trial device documentation of delivery. The principal investigator(s) or designee will take inventory of the product and complete the delivery documentation with receipt date, condition of the device and signature. Both the trial site and the trial Sponsor will retain copies of these documents.

The investigator will maintain a Device Accountability Log of all trial devices received for use during this clinical trial. The log will be kept with the documents for the clinical trial and will be available for review during Trial Sponsor monitoring visits.

